1.5 Clinical Data to Date

Clinical experience with Alisertib includes phase 1 and 2 studies in both solid tumors and heme-lymphatic malignancies, described below.

Alisertib for clinical studies is being developed in 3 dosage formulations: powder-in-capsule (PIC), enteric-coated-tablet (ECT), and oral solution (OS: for pediatric use). The initial studies employed the PIC formulation, and more recent studies have evaluated safety, PK, relative bioavailability (in reference to the PIC), and antitumor activity after administration of the ECT formulation.

Using the ECT formulation, the dose-escalation, phase 1 portion of an ongoing study, C14007, has evaluated multiple dose levels from 10 to 60 mg BID for 7 days in repeat, 21-day cycles and 50 mg BID has been determined to be the MTD.

In Study C14007, which includes a phase 1 dose escalation using the same ECT formulation employed in this study, multiple dose levels up to 840 mg total cycle dose (60 mg BID for 7 days) were evaluated. At the maximum administered dose of 60 mg BID for 7 days

administered to patients with advanced solid tumors, 3 patients (out of 3 enrolled) developed myelosuppression during the treatment-free period which was considered intolerable and above the MTD of 50 mg BID. In summary, 700 mg total cycle dose (e.g., 50 mg BID administered daily for 7 days) represents the ceiling for dose escalation in these combinations with Alisertib planned for this current study.

The predominant toxicities reflect the mechanism of action in proliferating tissue (bone marrow, GI epithelium, and hair follicles). The suggested management of these toxicities is based on standard clinical paradigms for an anti-proliferative chemotherapeutic agent. Using a treatment-free period for recovery between each cycle of drug administration, the clinical experience from multiple phase 1 through 2 studies indicate that major toxicities can be managed to allow repeat treatment cycles over periods extending beyond 12 months.

Alisertib is structurally related to the benzodiazepines (BZD) (e.g., diazepam, lorazepam) and also has activity against the GABA α 1 BZD receptor. BZD-like effects (e.g., somnolence, confusion, memory loss) have been observed to be associated with the onset of maximal plasma concentration (e.g., T_{max} [time to maximum plasma concentration]). CNS effects associated with peak plasma levels have been generally managed by administration of divided doses (e.g., BID administration), although dose reductions have sometimes been required. While CNS effects attributed to Alisertib were also generally reversible and manageable by dose delay or reduction, the causal relationship, and thus optimal approach to management, were sometimes confounded by diverse causes including, but not limited to, concomitant medications (e.g., narcotic analgesics, antianxiety medications), comorbidities (e.g., infection, anemia, electrolyte abnormalities), and progressive malignancy (e.g., brain metastases).

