1.3.2 Alisertib treatment

Alisertib will be administered by mouth, twice daily on days of radiation treatment during the course of FSRT. All patients will receive 10 days of Alisertib, concurrent with 10 daily radiation treatments. The first dose should be administered on the day of, but prior to, the first radiation treatment. The dose of Alisertib will be determined according to the protocol.

During the maintenance therapy period, Alisertib will be administered by mouth, at 50 mg twice daily from day 1 to day 7 of a 21-day cycle. All patients will receive up to 18 cycles, or until tumor progression.

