5.2 Treatment Regimen

Alisertib will be administered by mouth, twice daily on days of radiation treatment during the course of FSRT. All patients will receive 10 days of Alisertib, concurrent with 10 daily radiation treatments. The first dose should be administered on the day of, but prior to, the first radiation treatment. The dose of Alisertib will be determined according to the protocol.

During the maintenance therapy period, Alisertib will be administered by mouth, at 50 mg twice daily from day 1 to day 7 of a 21-day cycle. All patients will receive up to 18 cycles, or until tumor progression

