6.3 Dose escalation/de-escalation

Dose escalation will proceed within each cohort according to a “3+3 design”, as explained in the following scheme. Dose-limiting toxicity (DLT) is defined above. The toxicity assessment period is 30 days after the completion of the radiation therapy.

Dose Level	Alisertib dose
-1	10 mg BID
1	20 mg BID
2	30 mg BID
3	40 mg BID
4	50 mg BID (final dose level)

Number of Patients with DLT at a Given Dose Level[†]	Escalation Decision Rule
0 out of 3	Enter 3 patients at the next dose level.
≥ 2	Dose escalation will be stopped. This dose level will be declared the maximally administered dose (highest dose administered). Three (3) additional patients will be entered at the next lowest dose level if only 3 patients were treated previously at that dose.
1 out of 3	Enter at least 3 more patients at this dose level. 
 • If 0 of these 3 patients experience DLT, proceed to the next dose level.

	
 If 1 or more of this group suffer DLT, then dose escalation is stopped, and this dose is declared the maximally administered dose. Three (3) additional patients will be entered at the next lowest dose level if only 3 patients were treated previously at that dose.
≤1 out of 6 at highest dose level below the maximally administered dose	This is generally the recommended phase 2 dose. At least 6 patients must be entered at the recommended phase 2 dose.
†Dose escalation will be determined based on the occurrence of DLTs. For the purposes of determining whether to advance the Dose Level, DLTs will be counted by patient (i.e., a patient who experiences more than 1 DLT will be counted only once).	

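### Section 1.5 sets a 700 mg total cycle dose as the escalation ceiling, but levels 3 and 4 in section 6.3 total 800 and 1000 mg over the 10-day concurrent course, and no visible text reconciles them

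*Combined protocol and SAP*

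**What the plan says.** Section 1.5 describes study C14007, which tested doses of "10 to 60 mg BID for 7 days in repeat, 21-day cycles" and found that "50 mg BID has been determined to be the MTD". It gives that study's highest dose, 60 mg twice daily for 7 days, as a cycle total of 840 mg. It then states the limit for the present trial: a "700 mg total cycle dose (e.g., 50 mg BID administered daily for 7 days) represents the ceiling for dose escalation in these combinations". The scope is also stated, because the limit concerns escalation "in these combinations with Alisertib planned for this current study".

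The escalated phase follows a different schedule. Section 1.3.1 gives radiation on weekdays for 10 treatments. Section 5.2 says: "All patients will receive 10 days of Alisertib, concurrent with 10 daily radiation treatments". Appendix II confirms twice-daily dosing on radiation days only. Section 6.3 lists 20, 30, 40 and 50 mg twice daily as levels 1 to 4, with 10 mg twice daily as level -1. It adds: "The toxicity assessment period is 30 days after the completion of the radiation therapy".

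For this trial's own treatment, the visible text uses the word *cycle* only for maintenance. Maintenance is given "at 50 mg twice daily from day 1 to day 7 of a 21-day cycle" (section 1.3.2). It starts at that fixed dose, and section 6.4 allows reductions only.

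**The concern.** The ceiling is written as a total per cycle, but the only phase in which the dose escalates has no defined cycle and has 10 dosing days instead of 7. Anyone checking the ladder against the ceiling must decide how a 21-day cycle with 7 dosing days corresponds to a 10-weekday course. On the plain cumulative reading, two of the four planned upward levels are above the stated limit.

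At stake is whether a safety limit that the protocol sets for itself agrees with its own dose table. The medical monitor, the IRB and the data and safety monitoring committee should be able to hold the two side by side and find that they agree. At present they cannot. Section 1.6, whose title promises a dose rationale, does not link the 7-day experience to the 10-weekday course either.

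**Working it through.** **Inputs.** Ceiling of 700 mg and comparison figure of 840 mg: section 1.5. Dose levels: section 6.3. Ten dosing days, twice daily: sections 1.3.2 and 5.2. Weekday pattern: section 1.3.1. Thirty days without treatment after radiation: schema in the Study Summary.

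**1. The plan's own figures.** Total = mg per dose × 2 doses per day × dosing days.
- 50 × 2 × 7 = 700 mg
- 60 × 2 × 7 = 840 mg

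Both printed figures reproduce exactly.

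**2. The same formula over the concurrent course.** Total = mg per dose × 2 × 10.

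| Level | Dose, twice daily | mg per day | 10-day total | Share of 700 mg | Running total first above 700 mg |
|---|---|---|---|---|---|
| -1 | 10 mg | 20 | 200 mg | 29% | never |
| 1 | 20 mg | 40 | 400 mg | 57% | never |
| 2 | 30 mg | 60 | 600 mg | 86% | never |
| 3 | 40 mg | 80 | 800 mg | 114% | dosing day 9 (80 × 8 = 640; 80 × 9 = 720) |
| 4 | 50 mg | 100 | 1000 mg | 143% | dosing day 8 (100 × 7 = 700; 100 × 8 = 800) |

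Levels 3 and 4 exceed 700 mg by 100 mg and 300 mg.

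**3. Does the course fit in one 21-day period?** Ten consecutive weekdays span 12 calendar days from a Monday start and 14 from any other weekday. If the 3 days of interruption that section 1.3.1 permits are counted as treatment days, the course covers 13 weekdays, which span 17 to 19 days. In each case the whole total falls within 21 days. The 30 treatment-free days that follow are longer than 21, so no 21-day window holds doses from both the concurrent course and maintenance. The excess therefore comes from the concurrent course alone.

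**4. The per-dose reading.** If the limit is 50 mg twice daily, whatever the number of days, level 4 equals it and no level exceeds it. The sentence does not say this, however. The 700 mg total is the stated limit, and 50 mg twice daily for 7 days is offered only as an example of it.

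**5. Maintenance.** 50 × 2 × 7 = 700 mg per 21-day cycle, which meets the ceiling exactly. Maintenance is not escalated, so it cannot be what a ceiling for dose escalation governs.

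**The case against.** The strongest reply is that section 1.5 is background and decides nothing. Sections 6.3, 7.2 and 8.4 base escalation on counts of dose-limiting toxicities within a fixed ladder and never refer to the ceiling. The top level is 50 mg twice daily in both the schema and section 6.3, and it equals the earlier maximum tolerated dose. Under section 10.1 the medical monitor reviews the data at each new level before escalation. A reader is therefore not left in doubt about the highest planned dose. All of this stands, and it limits the practical effect. It does not remove the mismatch, because the sentence says that it applies to escalation in this trial.

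Three stronger readings are tempting, and the documents do not support them.

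- *The ceiling has no unit or scope.* It has both: milligrams per cycle, as for the 840 mg figure, and escalation in this study's combinations. What is missing is how a cycle corresponds to the 10-day course.
- *Levels 3 and 4 are shown to be intolerable, because 1000 mg is above the 840 mg at which all three patients had intolerable myelosuppression.* That result comes from 60 mg twice daily for 7 days, a higher daily dose on a different schedule. It does not establish what 10 weekdays at a lower daily dose would do.
- *The ceiling is exceeded on any basis.* It is not exceeded on the per-dose reading. Counting per calendar week, or averaging over the observation period, would also clear every level, but the documents nowhere offer those bases and they carry no weight here.

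**Conclusion.** The point holds as an unreconciled mismatch between section 1.5 and sections 5.2 and 6.3. On the cumulative reading that its words carry, the 700 mg ceiling is exceeded by level 3 at 800 mg (114%) and level 4 at 1000 mg (143%). If a per-dose limit was intended, the ladder complies and the sentence is misworded. Either way some text must change.

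This rests on 10 full dosing days, no weekend treatment, and a course completed within 21 days. Interruptions longer than the permitted 3 days could spread it further. It also rests on the visible text: section 3.1 shows only a heading, and the Investigator's Brochure to which the protocol refers was not available.

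A reader might infer that the ladder is the side in error, or that the ceiling is. The documents do not settle that. Nor does this point say that any level is unsafe. It should be fixed, but it does not alter the escalation rule, the definition of dose-limiting toxicity or the analysis.

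**What to change.** Reconcile sections 1.5, 5.2 and 6.3 (and section 1.3.2, which repeats 5.2) so that the stated ceiling and the escalation ladder agree on one explicit basis that covers the 10-day concurrent course. The text should say whether the limit is per dose or cumulative and, if cumulative, over what period. A short rationale in section 1.5 or 1.6 for carrying the 7-day experience over to 10 weekdays would help. No dose, schedule or limit is proposed here; that choice belongs to the sponsor-investigator.

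If reconciliation only clarifies wording, the cost is a brief text amendment, with no change to the toxicity rules, analysis, patient number or visits. If it led to a change in the ladder, the estimate of up to 24 patients in section 7.1 would need to be checked again.

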1.6 Dose Rationale and Risk/Benefits

The safety risks of Alisertib treatment are: (1) leukopenia, neutropenia, febrile neutropenia, and lymphopenia with a potential increased susceptibility to infection; (2) thrombocytopenia with a potential increased risk of bleeding; (3) anemia; (4) gastrointestinal (GI) toxicity resulting in stomatitis/mucositis, nausea, vomiting, anorexia, abdominal pain, dyspepsia, diarrhea, dehydration, and potentially mucosal/GI bleeding, and sepsis; (5) alopecia; (6) asthenia/fatigue; (7) fever; and (8) benzodiazepine-like effects including sedation, somnolence, sleep disorders, confusion, disorientation and associated memory loss and gait disturbances (which were reversible in clinical studies with cessation of treatment or dose reduction). Skin changes including hand-foot syndrome have been reported in some patients. Clinical safety data includes experience from patients who received multiple cycles followed by treatment-free periods between each cycle, and from patients who reduced or discontinued treatment. Based on the available clinical data, drug abuse, dependency, and withdrawal were not observed.

While these toxicities are potentially associated with risk or discomfort to the patient, they are anticipated to be reversible. Alisertib has not led to major neurotoxicities or fluid retention as a single agent. However, because there is only limited human experience with Alisertib, it is possible that Alisertib will have other toxicities that have not been observed in, or predicted based on, rat, dog, and human studies. Alisertib has a low potential to prolong the QT interval in vivo based upon its extremely weak in vitro binding to hERG (IC₅₀ and K_i both > 100 μ M).

To mitigate the inherent risks in clinical studies of Alisertib, patients are evaluated frequently while they are receiving treatment.

Because Alisertib inhibits Aurora A kinase, it is possible that Alisertib may interfere with cancer growth and cause cancer cell death through a potentially non-cross resistant pathway as compared to other agents that patients may have received. The clinical utility of these effects will be investigated in current and future studies.

2.0 Study Objective

2.1 Primary Objectives:

[figure not shown]
1. Evaluate the safety and tolerability of the study treatment
2. To determine the Maximum Tolerated Dose (MTD) of daily oral ALISERTIB when combined with fractionated stereotactic radiation treatment for recurrent high grade glioma.

2.2 Secondary Objectives:

1. To estimate 6 month progression free survival rate
2. To estimate the medial time to progression
3. To estimate overall survival
4. To estimate the impact of quality of life (QoL)

3.0 STUDY DESIGN

3.1 General Design

3.2 Primary Study Endpoints

1. Evaluate the safety and tolerability of the study treatment
2. To determine the Maximum Tolerated Dose (MTD) of daily oral ALISERTIB when

combined with fractionated stereotactic radiation treatment for recurrent high grade glioma.

3.3 Secondary Study Endpoints

1. To estimate 6 month progression free survival rate
2. To estimate the median time to progression
3. To estimate overall survival
4. To estimate the impact of quality of life (QoL)

3.4 Primary Safety Endpoints

To determine the Maximum Tolerated Dose (MTD) of daily oral ALISERTIB when combined with fractionated stereotactic radiation treatment for recurrent high grade glioma.

4.0 SUBJECT SELECTION AND WITHDRAWAL

4.1 Inclusion Criteria

1. Patients must have a previously histologically or cytologically confirmed high grade glioma (astrocytic or oligodendroglial supratentorial tumors grade 3 or 4) that has been previously treated with fractionated radiation therapy and now shows evidence of recurrence.
2. Patients must have recovered from the toxic effects of prior therapy.
3. Patients must have recovered from the effects of surgery. There must be a minimum of 21 days from the day of surgery to the day of protocol treatment. For core or needle biopsy, a minimum of 7 days must have elapsed prior to the day of protocol treatment.
4. Prior treatment with cytotoxic and biological agents is permissible. There should be at least a 2-week break between prior treatment and the protocol treatment.
5. Prior treatment with fractionated radiation therapy (up to 60Gy) is an eligibility criterion, however there should not have been a second course of fractionated radiotherapy to the supratentorial area.
6. One prior single fraction radiosurgical procedure within the treatment field is acceptable if $V12 < 5$ cc (V12 is the volume of normal brain (outside GTV) receiving 12 or more Gy). Additional radiosurgical procedures outside of the treatment area are acceptable.
7. Subject must be able to take oral medication and to maintain a fast, is required for 2 hours before and 1 hour after MLN8237 administration.
8. $ANC > 1500/mm^3$, platelets $> 100,000/mm^3$, Hgb > 9 g/dL. Values must be obtained without need for myeloid growth factor or platelet transfusion support within 14 days of registration. However, erythrocyte growth factor is allowed as per published ASCO guidelines.
9. Total bilirubin \leq ULN, SGOT (AST) and SGPT (ALT) $< 1.5 \times$ ULN, within 14 days of registration.
10. Adequate renal function as defined by: calculated creatinine clearance must be ≥ 40 mL/minute (Cockcroft-Gault), within 14 days of registration.
11. Age > 18 years.
12. ECOG performance status < 2 (see Appendix I).
13. Life expectancy of greater than 2 months.
14. Women of childbearing potential must have a negative β -HCG pregnancy test documented within 7 days prior to registration.

15. Women of child-bearing potential and men must agree to use adequate contraception (hormonal or barrier method of birth control; abstinence) prior to study entry and for 4 months after last dose.
16. Ability to understand and the willingness to sign a written informed consent document.

4.2 Exclusion Criteria

1. Known history of uncontrolled sleep apnea syndrome and other conditions that could result in excessive daytime sleepiness such as severe chronic obstructive pulmonary disease requiring supplemental oxygen.
2. Systemic infection requiring IV antibiotic therapy within 14 days preceding the first dose of study drug, or other severe infection.
3. Myocardial infarction within 6 months prior to enrollment, New York Heart Association (NYHA) Class III or IV heart failure, uncontrolled angina, severe uncontrolled ventricular arrhythmias, or electrocardiographic evidence of acute ischemia or active conduction system abnormalities. Prior to study entry, any ECG abnormality at Screening has to be documented by the investigator as not medically relevant.
4. Female subject is pregnant or breast-feeding. Confirmation that the subject is not pregnant must be established by a negative serum human chorionic gonadotropin (hCG) pregnancy test result obtained during screening. Pregnancy testing is not required for post-menopausal or surgically sterilized women.
5. Patient has received other investigational drugs within 14 days before enrollment
6. Serious medical or psychiatric illness likely to interfere with participation in this clinical study.
7. Other severe acute or chronic medical or psychiatric condition, including uncontrolled diabetes, malabsorption, resection of the pancreas or upper small bowel, requirement for pancreatic enzymes, any condition that would modify small bowel absorption of oral medications, or laboratory abnormality that may increase the risk associated with study participation or investigational product administration or may interfere with the interpretation of study results and, in the judgment of the investigator, would make the patient inappropriate for enrollment in this study.
8. Treatment with clinically significant enzyme inducers, such as the enzyme-inducing antiepileptic drugs phenytoin, carbamazepine or phenobarbital, or rifampin, rifabutin, rifapentine or St. John's wort within 14 days prior to the first dose of MLN8237 and during the study.
9. Known history of human immunodeficiency virus (HIV) infection, hepatitis B, or hepatitis C. Testing is not required in the absence of clinical findings or suspicion.
10. Patients have a history of any other malignancy from which the patient has been disease-free for less than 2 years, with the exception of adequately treated basal or squamous cell carcinoma of skin, superficial bladder cancer or carcinoma in situ of cervix, AJCC (version 7.0) stage 0 or I breast cancer, AJCC (version 7.0) stage I, or II prostate cancer.
11. Radiation therapy to more than 25% of the bone marrow. Whole pelvic radiation is considered to be over 25%.
12. Patients who cannot swallow whole tablets (i.e. medication tablets)

4.3 Gender/Minority/Pediatric Inclusion for Research

This study includes both genders and minority patients. Pediatric patients are excluded.

4.4 Subject Recruitment and Screening

Patients who are 18 years of age or older with high grade gliomas are eligible for the study. Patients can be recruited from PI or co-investigators' clinical practices. Principal Investigator and research nurses/research associates should be notified of potential study subjects. Appropriate laboratory or diagnostic testing necessary to meet any noted inclusion or exclusion criteria will be ordered through the recruiting physician. PI of the study or study designated research nurse/research associate will screen and determine the final eligibility of the subject for enrollment.

4.5 Early Withdrawal of Subjects

4.5.1 When and How to Withdraw Subject

Patients will be informed that they have the right to withdraw from the study at any time for any reason, without prejudice to their medical care. The investigator also has the right to withdraw patients from the study for any of the following reasons:

1. Intercurrent illness
2. Occurrence of an unacceptable adverse event
3. A treatment delay >3 weeks
4. Patient request
5. Protocol violations based on the judgment of PI
6. Non-compliance
7. Administrative reasons
8. Failure to return for follow-up
9. General or specific changes in the patient's condition that make it unacceptable to continue treatment, in the judgment of the investigator
10. Progressive disease

At the time of withdrawal, all study procedures outlined for the End of Study visit should be completed. The primary reason for a patient's withdrawal from the study is to be recorded in the source documents.

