4.5.2 Data Collection and Follow-Up for Withdrawn Subjects

According to FDA regulations, when a subject withdraws from the study, the data collected on the subject to the point of withdrawal remains part of the study database and may not be removed.

A subject who discontinues study treatment needs to state whether he/she wishes to continue participating in the study and allow further data collection as part of long term follow-up. Subjects who choose to continue with the study will participate in follow-up visits and evaluations according to the protocol. Subjects who refuse to participate in follow-up will be withdrawn from the study.

Study data collected prior to a subject's withdrawal from the study will be included in the study analysis.

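### Section 4.5.1 allows withdrawal from the study, not only from treatment, at progression, and nothing requires survival status afterwards, so overall survival could be informatively censored

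*Combined protocol and SAP*

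**What the plan says.** Section 4.5.1 states: "The investigator also has the right to withdraw patients from the study for any of the following reasons". Ten reasons follow, and the last is "10. Progressive disease". The same section adds: "At the time of withdrawal, all study procedures outlined for the End of Study visit should be completed". It mentions no later contact for survival.

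Section 4.5.2 deals with stopping treatment: "A subject who discontinues study treatment needs to state whether he/she wishes to continue participating in the study and allow further data collection". For those who agree, "Subjects who choose to continue with the study will participate in follow-up visits and evaluations according to the protocol". Those who decline are withdrawn. Data gathered before a withdrawal stay in the analysis; nothing is said about survival data after it.

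Sections 1.3.2 and 5.2 make tumor progression an end point of maintenance treatment. They do not make it the end of study participation.

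Section 3.3 lists "To estimate overall survival" among the secondary endpoints. Section 7.2 counts survival from the start of radiation, plans a Kaplan-Meier median for patients at the MTD, and says that the estimates will feed sample size work for a later phase II trial. It has no censoring rule for survival.

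**The concern.** Sections 4.5.1 and 4.5.2 draw the line in different places. Under 4.5.2, a patient who stops treatment at progression is asked about continuing and can be followed. Under 4.5.1, the investigator may instead take the same patient off the study for that same event. The text does not say which route applies, or that a patient withdrawn by the investigator is still given the choice in 4.5.2.

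If a patient leaves the study at progression and no later survival status is sought, the natural Kaplan-Meier handling is to censor at that date. Kaplan-Meier assumes that censored patients have the same future risk as those who remain. A patient who has just progressed has a higher risk of death than one who has not, so the censoring is informative and the estimated median is too high. At stake is a descriptive survival estimate that the plan intends to carry into the design of another trial.

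**Working it through.** **Is the gap closed elsewhere?**

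- Section 9.1 seeks vital status, but only for subjects who revoke authorization to use their health information.
- Section 8.1 (post-study adverse events) asks for notice of deaths after a subject leaves the study only if they may be related to the study. Deaths from the tumor fall outside it.
- Appendix II schedules visits beyond year 1 but has no survival contact for patients who are off study.
- Appendix VI has a death report form, but nothing says that vital status is to be sought after withdrawal.

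No section requires survival status after withdrawal for progression.

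**Size of the effect.** The plan has no survival figure to reproduce, so this is an illustration on assumed inputs.

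- Median time to first event (progression or death): 4 months, so h = ln 2 / 4 = 0.1733 per month.
- Median survival after progression: 6 months, so m = ln 2 / 6 = 0.1155 per month.
- Share of first events that are deaths: d = 0.10.
- Share w of progressing patients withdrawn and censored at progression, chosen at random: varied.

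True survival is S(t) = e^(−ht) + [h(1−d)/(h−m)] × (e^(−mt) − e^(−ht)). The bracketed factor is 0.1733 × 0.9 / 0.0578 = 2.70. At t = 11.1, S = 0.146 + 2.70 × (0.277 − 0.146) = 0.50, so the true median is 11.1 months.

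With withdrawal, the proportions still at risk are:

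- not progressed: P0(t) = e^(−ht)
- progressed and still followed: P1(t) = (1−w) × 2.70 × (e^(−mt) − e^(−ht))

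Kaplan-Meier then tracks the hazard λ(t) = [h·d·P0 + m·P1] / (P0 + P1). Its median is the time at which the integral of λ reaches ln 2.

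| Share withdrawn at progression | Kaplan-Meier median (months) | Shift (months) |
|---|---|---|
| 0% | 11.1 | 0 |
| 10% | 11.4 | 0.3 |
| 25% | 11.9 | 0.8 |
| 50% | 13.2 | 2.1 |
| 100% | 40.0 | 28.9 |

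The last row is a limiting case. With every progressing patient censored, only deaths without progression count, the hazard is h·d, and the median is 4 / 0.10 = 40 months. It follows directly from the assumed 10%.

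**Sensitivity.** A second version uses the historical series in Section 1.2.2: 30% progressed at 3 months (h = −ln 0.70 / 3 = 0.119 per month), with median survival of 10 to 11 months. With d between 5 and 20% (assumed), the median becomes about 11.1-12.4 months at 25% withdrawn and 12.8-14.8 at 50%. If 45% progress by 3 months (assumed), the median at 50% withdrawn is about 11.2-13.1. The bias was upward whenever any patients were withdrawn.

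**Set against sampling error.** Under the first set of inputs, with 7 patients and complete follow-up, 95% of simulated Kaplan-Meier medians fall between about 5 and 22 months.

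**The case against.** The other side has a good deal to say. Withdrawal is a right of the investigator and is not automatic, and no text says that survival is censored at progression. Progression ends maintenance treatment under Sections 1.3.2 and 5.2, so these patients are the ones to whom 4.5.2 offers follow-up, under a heading that names withdrawn subjects. Appendix II runs follow-up every 3 months to year 2 and every 4-6 months after that, past the 18 × 21 = 378 days of maintenance. The off-study form in Appendix VI records last dose, start and end of follow-up, off-study date and last contact separately, and progression is not among its named reasons for going off study, although there is an open category. The endpoint is secondary and descriptive, with very few patients.

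All of this stands, and it rules out the stronger reading that a reader might infer: that the plan censors survival at progression for nearly everyone and would report a median near 40 months. That needs every progressing patient to be withdrawn, which 4.5.2 makes implausible. A reader might also infer that optional withdrawal makes the censoring more selective by prognosis. The documents give no basis for that, and the calculation, which withdraws patients at random, does not test it.

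The objection does not remove the conflict. Section 4.5.1 still permits study withdrawal for progression, and no section requires survival status after it. Wide intervals do not correct a bias whose direction is known.

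**Conclusion.** The point holds as an unreconciled pair of sections together with a missing censoring rule. Survival could be censored at progression for some patients, and any such censoring would push the Kaplan-Meier median upward. Under the stated inputs the shift is about 0.3 months at 10% withdrawn, 0.8 at 25% and 2.1 at 50%; calibrated to the protocol's historical series it is about 1.0-1.4 months at 25% and 2.6-3.8 at 50%. It is zero if nobody is withdrawn.

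These sizes rest on exponential times, random withdrawal, an assumed share of deaths without progression and an assumed share withdrawn. They show direction and range and do not predict what the trial will report. At low withdrawal shares the shift is small beside the sampling error expected with 6-8 patients at the MTD, and the MTD and dose-limiting toxicity assessment does not depend on it. The change is worth making because it is cheap and the estimate is meant to inform phase II planning.

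**What to change.** 1. Reconcile Section 4.5.1 with 4.5.2 so that progressive disease is not by itself a reason to end study follow-up. The rules on stopping treatment need not change.
2. State in 4.5.2 that survival status is collected by phone or from records until death, withdrawal of consent or the end of the study, including for patients whom the investigator withdraws.
3. In Section 7.2, define overall survival as censored at the date last known alive.

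The cost is a few sentences and a small amount of extra follow-up work. No visit, test or procedure is added.
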